### **15.5 Investigator Responsibilities**

By signing the Agreement of Investigator form, the Investigator agrees to:

1. Conduct the study in accordance with the protocol and only make changes after notifying the Sponsor (or designee), except when to protect the safety, rights or welfare of subjects.
2. Personally conduct or supervise the study (or investigation).
3. Ensure that the requirements relating to obtaining informed consent and IRB review and approval meet federal guidelines, as stated in § 21 CFR, parts 50 and 56.
4. Report to the Sponsor or designee any AEs that occur in the course of the study, in accordance with §21 CFR 312.64.
5. Ensure that all associates, colleagues and employees assisting in the conduct of the study are informed about their obligations in meeting the above commitments.
6. Maintain adequate and accurate records in accordance with §21 CFR 312.62 and to make those records available for inspection with the Sponsor (or designee).
7. Ensure that an IRB that complies with the requirements of §21 CFR part 56 will be responsible for initial and continuing review and approval of the clinical study.
8. Promptly report to the IRB and the Sponsor (or designee) all changes in the research activity and all unanticipated problems involving risks to subjects or others (to include amendments and IND safety reports).
9. Seek IRB approval before any changes are made in the research study, except when necessary to eliminate hazards to the patients/subjects.
10. Comply with all other requirements regarding the obligations of clinical

Title: The Role of Topical Antibiotic Prophylaxis in Oculofacial Plastic Surgery: A Randomized Controlled Pilot Study.

NCT number: NCT03199911

Document date: 4/1/2020

Statistical Analysis Plan (SAP)

The Role of Topical Antibiotic Prophylaxis in Oculofacial Plastic Surgery: A Randomized Controlled Pilot Study.

Principal Investigator

[name]

Professor of Ophthalmology

Department of Ophthalmology

University of California, San Francisco

San Francisco, CA 94143

Protocol identification number

IRB 17-22309

ClinicalTrials.gov identifier

NCT03199911

Author

[name] MD

Clinical Instructor and Fellow

Department of Ophthalmology

University of California, San Francisco

[figure not shown]
San Francisco, CA 94143

SIGNATURE PAGE

A handwritten signature in black ink, consisting of several overlapping loops and a long horizontal stroke extending to the right.

Principal Investigator

[name] (4/1/2020)

A handwritten signature in black ink, appearing to read '[name]' in a cursive style.

Author

[name] (4/1/2020)

Table of contents

| | |
|---|---|
| 1. Introduction..... | 5 |
| 2. Study design | 5 |
| 2.1 Sample size calculation..... | 5 |
| 3. Aims and objectives..... | 5 |
| 4. Outcomes | 6 |
| 4.1 Primary outcome | 6 |
| 4.2 Secondary outcomes | 6 |
| 4.3 Safety outcomes | 6 |
| 5. Populations and subgroups to be analyzed | 6 |
| 5.1 Populations..... | 6 |
| 5.2 Subgroups..... | 6 |
| 6. Analyses..... | 6 |
| 6.1 Primary outcome | 6 |
| 6.2 Secondary outcomes | 6 |
| 7. Missing data | 6 |
| 8. References..... | 7 |

1. Introduction

There is no consensus on the need for topical antibiotic prophylaxis after routine periocular surgery. This study is intended to act as a pilot to determine whether non-antibiotic ointment has a higher risk of infection than antibiotic ointment.

This statistical analysis plan (SAP) will give more detailed descriptions of the endpoints in the study and the corresponding analyses.

2. Study design

This is a randomized, unmasked clinical trial. Participants are recruited from the Oculofacial Plastic Surgery clinic at UCSF after deciding to proceed with periocular surgery. Inclusion and exclusion criteria are as detailed in the study protocol. The recruitment target is 400 individuals, approximately 200 per arm, based on the expected institutional surgical volume of eligible patients over a 2 year period.

The study is a parallel-group RCT with two arms spanning approximately 24 months. Participants were randomized to receive either topical antibiotic ointment or topical non-antibiotic ointment for a 7 day course after routine periocular surgery.

Outcomes were assessed at the first post-operative visit, approximately 1-2 weeks after surgery.

2.1 Sample size calculation

The primary outcome measure for the power calculation is the difference in surgical site infection frequency between the antibiotic and non-antibiotic arms.

| Sample Size per Arm | | Infection Rate (No Antibiotics) | | |
|-----------------------------------|------|---------------------------------|-------|-------|
| | | 0.7% | 2% | 4% |
| Infection Rate (With Antibiotics) | 0% | 1,388 | 483 | 239 |
| | 0.1% | 2,056 | 551 | 255 |
| | 0.2% | 3,200 | 633 | 273 |
| | 1% | 15,358 | 2,515 | 489 |
| | 2% | 1,386 | N/A | 1,239 |
| | | | | |

Based on these calculations, a non-inferiority study was deemed to be infeasible based on institutional surgical volume. Therefore, the decision was made to select a sample size approximating the surgical volume of eligible patients over a 2 year period in order to serve as a pilot study to detect whether a clinically relevant difference in infections occurred. For clean wounds, an infection rate greater than 5% is considered unacceptable(1-3); therefore, this sample size allowed 87% power at a 95% confidence level to detect a difference between an expected infection rate of 0.2% with antibiotics versus a maximum acceptable rate of 5% without antibiotics.

3. Aims and objectives

To study whether topical antibiotic prophylaxis significantly reduces the rate of infection after oculofacial plastic surgery.

4. Outcomes

This section will present the outcomes investigated to answer the study aims and objectives. The analyses are described in section 6 Analyses.

4.1 Primary outcome

Frequency of surgical site infection (superficial and deep incisional)

4.2 Secondary outcomes

Frequency of wound complications

Allergic contact dermatitis

Wound dehiscence

Frequency of surgical site infection (superficial and deep incisional) among subgroups (low- versus high-risk patients for infection)

4.3 Safety outcomes

Adverse events

Adverse events are reported at each clinic visit.

Concomitant medications

Usage of medications during study period will be recorded.

5. Populations and subgroups to be analyzed

5.1 Populations

Intention-to-treat (ITT)

All randomized study subjects. This will be seen as the primary population for the analysis.

5.2 Subgroups

Low- versus high-risk for infection patients (listed as secondary outcome)

6. Analyses

Continuous outcomes will be presented with descriptive statistics; normally distributed data by the mean and standard deviation (SD). Binary and categorical variables will be presented using counts and percentages. R version 4.0.0 will be used for all statistical analysis.

The subsections below will describe analyses in addition to the descriptive statistics.

6.1 Primary outcome

The primary analysis will compare intervention groups using Fisher's exact test due to the expected small sample size of the outcome. A risk ratio will be computed and 95% confidence intervals will be presented.

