## 1 BACKGROUND AND RATIONALE

Despite a lack of evidence supporting the use of routine topical antibiotic therapy (e.g. poly-bacitracin, bacitracin, erythromycin, etc.) after eyelid surgery, it is currently standard of care to provide patients with post-operative antibiotics in order to prevent surgical site infections (SSIs). For instance, a 2014 survey of oculoplastic surgeons from 43 countries revealed that while rates of prophylactic oral and perioperative intravenous antibiotic use varied considerably, topical antibiotic use was common across all geographic regions (85.2%).

The rates of postoperative infections involving Class I: Clean and Class II: Clean-Contaminated\* surgical wounds, including those associated with eyelid surgery, are known to be low. For instance, while the rate of infection after blepharoplasty is 0.2% with antibiotic ointment use and the rate of infection after external dacryocystorhinostomy is 1% with antibiotic use, the rates of infection without topical antibiotics in a range of dermatological procedures such as Mohs surgery are as low as 0.7%. There is currently no literature on the rates of infection after blepharoplasty and other eyelid-specific procedures in the absence of prophylactic antibiotic ointment.

As antibiotic resistance, antibiotic-related complications (e.g. contact dermatitis), and healthcare costs are on the rise, it has been advocated that topical antibiotic prophylaxis be withheld in eyelid surgery except in certain high risk cases. As such, we propose a randomized control trial testing the hypothesis that routine topical antibiotic prophylaxis does not significantly reduce the rate of infection after eyelid surgery. The hope is to reduce rates of antibiotic resistance, antibiotic-related complications, and healthcare costs.

\*Under CDC surgical wound classification system, Class I/Clean wounds include “an uninfected operative wound in which no inflammation is encountered and...[is] primarily closed and, if necessary, drained with closed drainage...Class II/Clean-Contaminated wounds include those ...without unusual contamination... [and] no evidence of infection or major break in technique.”

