6.2 Secondary outcomes

The secondary analysis will compare intervention groups using Fisher's exact test due to the expected small sample size of the outcomes. A risk ratio will be computed and 95% confidence intervals will be presented.

7. Missing data

Missing data will not be imputed. Participants with missing data for baseline demographic and clinical characteristics will be reported as "Unknown." Participants missing the primary outcome will not be included in the primary analysis, and the reason for the missing outcome data will be included in the

patient flow diagram. Participants missing data for a secondary outcome will not be included in the analysis for that particular outcome.

8. References

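### The planned Fisher test is valid and matches the stated 87% power, but it is conservative at low infection rates; a pooled-Z unconditional exact test would usually add power at the same 5% level

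*SAP*

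**What the plan says.** SAP 6.1 sets the primary test and gives the reason: the arms are to be compared with Fisher's "exact test due to the expected small sample size of the outcome". It adds a risk ratio with a 95% confidence interval but does not say how the interval is formed. SAP 6.2 repeats the choice for the secondary outcomes: "exact test due to the expected small sample size of the outcomes".

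SAP 2.1 says that "this sample size allowed 87% power at a 95% confidence level" for "an expected infection rate of 0.2% with antibiotics versus a maximum acceptable rate of 5% without antibiotics". It names neither the test behind that figure nor its sidedness. The target is 400 participants, about 200 per arm, set by expected surgical volume (SAP section 2). Participants without a primary outcome are left out of the primary analysis (SAP section 7), and withdrawals are not replaced (Protocol 11.3). Neither document discusses the true error rate of Fisher's test or any other exact test.

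**The concern.** Fisher's test conditions on the total number of infections. This trial does not fix that total. When it is small, few splits between the arms are possible, and the attainable p-values jump over 5%. The test then rejects less often than it is allowed to. A small event count, which the SAP gives as its reason for choosing Fisher, is where this cost is largest.

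Power matters here because recruitment is capped by surgical volume, and the SAP wants to detect a clinically relevant difference. The protocol's hypothesis is that prophylaxis does not significantly reduce infection, so a test that rejects less often than 5% allows makes a result in line with that hypothesis more likely. If another exact test keeps the same error guarantee and rejects more often when a difference exists, it offers extra power without extra patients.

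**Working it through.** **Inputs.** 200 per arm (SAP 2; Protocol 13.6). Rates: 0.2% v 5% (SAP 2.1 text); 2% and 4% without antibiotics (SAP 2.1 table). The protocol background gives two rates with antibiotics: "the rate of infection after blepharoplasty is 0.2% with antibiotic ointment use" and "the rate of infection after external dacryocystorhinostomy is 1% with antibiotic use". Level: 5%; two-sided is an assumption. No dropout rate is given, so other arm sizes are tried as a range.

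**Method.** Let x and y be the infections with and without antibiotics, in arms of n1 and n2. For a rejection region R, the power is the sum over R of Bin(x; n1, p1) × Bin(y; n2, p2), enumerated in full. The true error rate is the same sum with p1 = p2.

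**Step 1: the SAP's own figure.** Two-sided Fisher, p ≤ 0.05, 200/200, 0.2% v 5%: 87.1%. The stated 87% reproduces. The pooled normal approximation gives 85.7%, one-sided 5% Fisher 92.8%, the continuity-corrected approximation 77.4% and the arcsine formula 95.1%. Two-sided Fisher is the closest match.

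**Step 2: the alternative test.** Z = (y/n2 − x/n1) / √[p̄(1 − p̄)(1/n1 + 1/n2)], with p̄ = (x + y)/(n1 + n2). The critical value is chosen so that the error rate, maximised over all common rates, is at most 5%. At 200/200 this means rejecting at |Z| ≥ 2.000; the maximum error rate is 4.96%.

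**Step 3: true error rate at 200/200.**

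| Common rate | Fisher | Share of 5% | Pooled-Z |
|---|---|---|---|
| 0.2% | 0.001% | near 0 | 0.10% |
| 0.7% | 0.16% | 3% | 2.6% |
| 1% | 0.49% | 10% | 4.0% |
| 2% | 1.72% | 34% | 4.3% |
| 2.6% (mean of 0.2% and 5%) | 2.08% | 42% | 4.1% |
| 5% | 2.89% | 58% | 4.6% |

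**Step 4: where the tests part.** For 0 v 5, Fisher's p = 2 × C(200,5)/C(400,5) = 0.061; for 0 v 6 it is 0.030. For 0 v 4, p̄ = 4/400 = 0.01 and Z = 0.02/√(0.01 × 0.99 × 0.01) = 2.01, which passes 2.000 (unconditional p = 0.047). Against zero infections, Fisher therefore needs 6 and pooled-Z needs 4. At 200/200, pooled-Z rejects every table that Fisher rejects.

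**Step 5: power at 200/200.**

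| Rates | Fisher | Pooled-Z |
|---|---|---|
| 0.2% v 5% | 87.1% | 93.9% |
| 0.2% v 4% | 70.9% | about 85% |
| 0.2% v 2% | 15.7% | 41.1% |
| 1% v 5% | 56.3% | 66.1% |

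Standard Boschloo gives 87.2% at 0.2% v 5%, almost no gain. With a Berger-Boos restriction (gamma 0.001) it gives 92.7%.

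**Step 6: other analysed arm sizes** (antibiotic/control; Fisher, then pooled-Z, gain in points).

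| Arms | 0.2% v 5% | 0.2% v 2% |
|---|---|---|
| 201/199 | 92.5%, 93.7% (1.2) | 27.5%, 40.7% (13.2) |
| 202/198 | 92.3%, 93.6% (1.3) | 27.2%, 40.3% (13.1) |
| 205/195 | 91.7%, 93.7% (2.0) | 26.1%, 39.3% (13.2) |
| 199/201 | 87.4%, 94.0% (6.6) | 15.9%, 41.5% (25.6) |
| 198/202 | 87.7%, 93.1% (5.4) | 16.2%, 28.6% (12.4) |
| 190/190 | 84.4%, 92.6% (8.2) | 13.5%, 38.5% (25.0) |
| 180/180 | 81.2%, 91.2% (10.0) | 11.5%, 35.7% (24.2) |
| 224/176 | 93.2%, 93.2% (0) | 34.5%, 34.5% (0) |

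The last row is an extreme imbalance, shown as the limiting case. At the unequal sizes from 201/199 to 198/202, a few tables are rejected by Fisher and not by pooled-Z. The nesting in Step 4 holds only for equal arms.

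**The case against.** The best defence is that nothing is wrong. Fisher's test is valid and widely used for rare events, the SAP gives its reason, and the stated power already includes the test's conservatism. Conditioning on the event total also has a respectable basis as a randomization test under the hypothesis of no effect. All of this stands.

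The second defence is that exactly equal analysed arms are unlikely. The SAP says about 200 per arm, no blocking is described, and missing outcomes are dropped. If 400 are analysed after simple 1:1 randomization (an assumption), average power at 0.2% v 5% is about 90.2% for Fisher and 93.7% for pooled-Z. The expected gain is then about 3.5 points, half of the 6.8 at 200/200. This also stands, and it limits the size of the point without removing it.

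Three stronger readings are tempting:

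- A reader might infer that Fisher uses only a tenth to a third of its 5% throughout. That holds only for common rates of 1% to 2%; Step 3 runs from near zero to 58%.
- A reader might infer that any unconditional exact test recovers the power. Standard Boschloo does not at 200/200.
- A reader might infer that five or fewer infections can never reach significance under Fisher. At 201/199, 0 v 5 already gives p = 0.030.

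The third defence is timing. The SAP is dated April 2020, describes randomization and outcome assessment in the past tense (section 2), and the trial is unmasked. A late move to a test that makes 0 v 4 significant could look data-driven. That stands as a condition on the fix.

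**Conclusion.** The point holds as a low-cost improvement. A reader might take it to mean that the 87% is wrong or that the primary test is invalid; the documents support neither, since the figure reproduces under the planned test. At 200/200 and a two-sided 5% level, the pooled-Z test adds 6.8 points at the SAP's own alternative, about 14 points at 0.2% v 4% and 25 points at 0.2% v 2%, with a maximum error rate of 4.96%.

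With arms within 5 of 200, or equal arms of 180 or 190, the gain in the cases tabulated is about 1 to 10 points at 0.2% v 5% and 12 to 26 points at 0.2% v 2%. It falls to nothing when the antibiotic arm is much the larger (224/176). When both rates are near 0.2%, events are too few for either test to come near 5%, and changing the test does not cure that. The conclusion assumes two-sided testing, which the SAP does not state, and independent binomial outcomes in each arm.

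**What to change.** **If no outcome data by arm have been seen:**

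- In SAP 6.1, name the two-sided 5% unconditional exact test with the pooled-Z statistic (Suissa-Shuster) as the primary test. State the statistic and the sidedness, because the gain depends on them.
- Report a confidence interval consistent with that test. One way is to invert the two-sided unconditional exact test of the risk ratio based on the score statistic, which equals pooled Z at a ratio of 1. State which arm is the denominator, since an arm may have no events.
- Keep Fisher's test as a labelled sensitivity analysis.
- In SAP 2.1, name the test and sidedness behind the power figure, and restate it for the chosen test over plausible analysed arm sizes.

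**If outcome data have been seen:** keep Fisher as primary and add the unconditional test as a labelled sensitivity analysis.

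SAP 6.2 need not change on the strength of these figures: they apply to the full arms, and the design does not fix arm sizes within the risk subgroups.

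**Cost:** SAP wording and probably an add-on R package; no extra patients, visits or data. The downsides are that readers know the test less well and that a late change needs a dated statement that no outcome data by arm had been seen.

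### The only planned between-arm estimate is a risk ratio with no direction, interval method or zero-cell rule, yet at the SAP's 0.2% rate the antibiotic arm has no infections in 67% of trials

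*SAP*

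**What the plan says.** SAP 6.1 plans Fisher's exact test for the primary outcome, because few events are expected, and then "A risk ratio will be computed and 95% confidence intervals will be presented". SAP 6.2 uses the same sentence for the secondary outcomes, which include infection in low- and high-risk subgroups. The opening of SAP section 6 adds descriptive output: "Binary and categorical variables will be presented using counts and percentages". No other between-arm estimate appears in the SAP.

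The planning section (SAP 2.1) works on a different scale. Its power measure is "the difference in surgical site infection frequency between the antibiotic and non-antibiotic arms", and the power statement contrasts "an expected infection rate of 0.2% with antibiotics versus a maximum acceptable rate of 5% without antibiotics". On size, SAP section 2 states: "The recruitment target is 400 individuals, approximately 200 per arm".

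The comparison is worded in both directions. The SAP introduction wants "to determine whether non-antibiotic ointment has a higher risk of infection than antibiotic ointment", which suggests no antibiotic over antibiotic. SAP section 3 asks "whether topical antibiotic prophylaxis significantly reduces the rate of infection after oculofacial plastic surgery", which suggests the reverse.

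Protocol 13.3 named a t-test or a linear regression on arm, whose coefficient would be a risk difference. Protocol section 13 says the SAP carries any modifications to that plan, and the SAP does not keep this analysis.

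**The concern.** The authors foresaw sparse events and adapted the test to them, but not the estimate. A risk ratio behaves badly when an arm is empty. With no antibiotic-arm infections it is 0 or infinite depending on direction, and with none in either arm it is 0/0. The usual log-scale interval then does not exist, and a score interval has at most one informative limit. Because no method is named, it could be chosen after the counts are known, in a trial where neither subjects nor investigators are blinded (Protocol 7.2).

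The ratio also does not speak directly to the SAP's own yardsticks, which are a difference in frequency and a maximum acceptable rate of 5% without antibiotics. SAP 2.1 judged a non-inferiority trial infeasible and called this a pilot, so estimates with intervals are a large part of what it can deliver. The report could end up with no usable interval for the excess infections or for the rate without antibiotics.

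**Working it through.** **Inputs.** n = 200 per arm (SAP 2). Antibiotic-arm rate 0.2% (SAP 2.1; Protocol section 1 cites it for blepharoplasty). Protocol section 1 also says "the rate of infection after external dacryocystorhinostomy is 1% with antibiotic use", and that procedure is enrolled too, so 1% is used as a second value and 0.5% as an assumed middle value. No-antibiotic rates 0.7% (a column of the SAP's table) and 5% (the power statement). Below, *a* v *b* means *a* infections with antibiotics and *b* without, each out of 200.

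**The plan's own figure.** Exact binomial enumeration of the two-sided Fisher test at 0.05, with 0.2% v 5% and 200 per arm, gives power 87.1%. The stated 87% is reproduced.

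**Chance of an empty arm**, P(zero) = (1 − p)^n:
- Antibiotic arm: 0.998^200 = 0.670; 0.995^200 = 0.367; 0.99^200 = 0.134. Expected count at 0.2%: 200 × 0.002 = 0.4.
- No-antibiotic arm at 0.7%: 0.993^200 = 0.245.
- At least one arm empty, with 0.7% without antibiotics: 1 − (1 − 0.670)(1 − 0.245) = 0.751. The same formula gives 0.522 at 0.5% and 0.347 at 1% with antibiotics.
- Both arms empty: 0.670 × 0.245 = 0.164 at 0.2% v 0.7%; 0.998^400 = 0.449 if both rates are 0.2%.
- Participants with a missing primary outcome are excluded and no dropout rate is given. If 160 to 190 per arm are analysed (an assumption), the 67% becomes 73% to 68%.

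**Zero cells when the trial succeeds.** Share of Fisher-significant results with no antibiotic-arm infections, at 5% without antibiotics:

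| Rate with antibiotics | P(significant and zero) | P(significant) | Share |
|---|---|---|---|
| 0.2% | 0.628 | 0.871 | 72% |
| 0.5% | 0.344 | 0.756 | 45% |
| 1% | 0.126 | 0.563 | 22% |

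**What the ratio interval then shows** (no antibiotic over antibiotic):
- 0 v 6, Fisher p = 0.030: the plain log interval cannot be computed. Adding 0.5 to each count gives 13 (0.74 to 229), which includes 1. The score interval is 1.58 to infinity (0 to 0.63 inverted), which excludes 1.
- 0 v 5, p = 0.061: adding 0.5 gives 0.61 to 198; the score interval is 1.32 to infinity. The two methods disagree again.
- 0 v 0: neither score limit is informative.

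**What the alternatives show at such counts:**
- Newcombe interval for the difference (no antibiotic minus antibiotic): 0 v 0 gives −1.9 to 1.9 percentage points; 0 v 3 gives 1.5 (−0.6 to 4.3).
- Clopper-Pearson interval for the no-antibiotic rate: 3/200 gives 0.31% to 4.32%; 4/200 gives 0.55% to 5.04%. The interval therefore lies below 5% with 3 or fewer infections, which has probability 0.947 at a true 0.7% and 0.431 at a true 2%.

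**Secondary outcomes.** Infections in a risk subgroup are a subset of the primary count, so an empty cell is at least as likely there. The documents give no rates for contact dermatitis or dehiscence, so nothing is claimed for those.

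**The case against.** The strongest reply is that 67% depends on 0.2% holding across the whole antibiotic arm. The Protocol gives that rate for blepharoplasty only and enrols a much wider mix. At 1% the figure is 13%, and at 2%, the highest antibiotic rate in the SAP's table, it is 1.8%. The infection definition (Protocol 4.1) lets its third criterion be met by a single sign such as redness, and assessment is unblinded, so counts could exceed the literature rates. This stands as a limit on the size of the problem. However, 0.2% is the rate the SAP itself planned on, and even at 1% at least one arm is empty in 35% of trials against 0.7%.

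Second, only the plain log interval fails, and the SAP does not commit to it. A one-sided score interval is valid, and its finite limit addresses whether risk is higher without antibiotics. That is true, but the SAP does not commit to a score interval either, and at 0 v 6 the choice decides whether 1 is excluded.

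Third, direction is a labelling matter, since the two ratios are reciprocals. That is largely right; it is the smallest part of the point.

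Fourth, readers can derive a difference and each arm's interval from the promised counts, and the plural in the SAP's sentence might cover more than the ratio. No data are lost, but a derivable interval is not a pre-specified one.

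Fifth, the SAP sets no rule for testing the no-antibiotic arm against 5%, and states that limit for clean wounds while the Protocol also admits clean-contaminated ones. The comparison should therefore be a description, not a new success criterion.

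**Conclusion.** The concern holds and should be fixed. On the SAP's own inputs (0.2%, 200 per arm) an empty antibiotic arm is the most likely outcome, at 67%. The planned interval is then not computable by the standard method, or open on one side, and its reading depends on a method the SAP does not name. The size depends on the true rate: 37% at 0.5% and 13% at 1%. The damage is confined to the estimate and its interval; the primary test and its power are sound. The protocol's regression would have given a difference, but the SAP, which carries the modifications, does not retain it.

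**What to change.** In SAP 6.1 and 6.2:
- Make the risk difference (no antibiotic minus antibiotic), with a 95% Newcombe interval, the main estimate.
- Report each arm's rate with a 95% Clopper-Pearson interval. For the primary outcome, set the no-antibiotic arm's interval, not the difference, beside the 5% limit.
- Keep the risk ratio as supplementary, reported whatever the counts, with its direction stated and a score interval that allows zero cells. Antibiotic over no antibiotic is the better direction: its denominator is zero in 25% rather than 67% of trials at 0.2% v 0.7%.
- State that Fisher's p-value governs if test and interval disagree.

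The cost is SAP wording and a few lines of R; design, sample size and test do not change. The drawback is occasional disagreement at the boundary. With no antibiotic-arm infections, Newcombe departs from Fisher only at 0 v 5 (lower limit +0.14 points, p = 0.061). With some infections in that arm it also does so in tables such as 1 v 7, 2 v 9 and 3 v 11, where the interval excludes 0 while p exceeds 0.05. Miettinen-Nurminen departs at both 0 v 4 (+0.09, p = 0.123) and 0 v 5 (+0.59), a modest reason to prefer Newcombe. The supplementary score ratio departs at the same two tables (lower limits 1.05 and 1.32).
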